6.1. Programming Environment

Unless otherwise specified, all analyses will be conducted using SAS® version 9.4 or later.

6.2. Analysis Groups

Unless otherwise specified, the statistical analyses will be presented by dose level in dose escalation phase and by arm in the dose expansion phase for the different analysis sets as defined in Section 5.

6.3. List of Data Display and Handling Appendices

Table 2 Overview of Data Display and Handling Appendices

Component
Appendix 2: Descriptive Statistical Summaries
Appendix 3: Data Display Conventions
Appendix 4: Study Day, Duration, Period, Visit and Analysis Windows
Appendix 5: Derived Data And Definitions
Appendix 6: Premature Withdrawals & Handling of Missing Data

7. Study Conduct and Study Population

7.1. Overview of Planned Analyses of Study Conduct and Study Population

Table 3 Overview of Planned Analyses of Study Conduct & Study Population

	Data Displays Generated		
	Table	Figure	Listing
Study Conduct			
Subject Disposition	Y		Y
Analysis Sets	Y		Y
Protocol Deviations	Y		Y
Demographics and Baseline Disease Characteristics			
Demographics and General Baseline Characteristics (Vital Signs, Body Measurements, Performance Status)	Y		Y
Cancer History & Characteristics	Y		Y
Prior Cancer Therapy	Y		Y
General Medical History by SOC and PT	Y		Y
Prior Non-cancer Therapies and Concomitant Therapies			
Prior Medications by ATC level II and PN	Y		Y
Concomitant Medications ATC level II and PN	Y		
Prior and Concomitant Procedures			Y
Exposure and Compliance			
Study Drug Exposure & Compliance	Y		Y
Infusion Interruptions & Dose Modifications	Y		Y

7.2. Study Conduct

7.2.1. Summary of Analysis Sets

The number and relative frequency of subjects in each analysis set as defined in Section 5 will be descriptively summarized.

- Number of screened subjects (percentage not to be calculated)
- Number of screen failures (percentage not to be calculated)
- Reason for screen failure (percentage not to be calculated, include non 0 categories only)
 - Adverse event
 - Death
 - Failure to meet continuation criteria
 - Logistical problem
 - Met eligibility criteria but not needed
 - Never dosed
 - Other
 - Physician decision
 - Pregnancy
 - Protocol-specified withdrawal criterion met
 - Screen failure
 - Screening not completed

QMS Document Name: Statistical Analysis Plan Template(EN)	Page 12 of 41
QMS No (include version ref): STF-015-GL.03	Document date: 14JUL2022
CONFIDENTIAL	

- Technical problems
- Withdrawal by parent/guardian
- Withdrawal by subject
- Withdrawal of consent
- COVID-19 Related
- Number of Enrolled Subjects (percentage not to be calculated)
- Safety Analysis Set (percentage not to be calculated)
- Dose-determining (DDS) Analysis Set
- Efficacy Evaluatable Analysis Set
- Pharmacokinetics Analysis Set
- [REDACTED]
- ADA Analysis Set

Percentages will be calculated with based on the number of subjects in the Safety Analysis Set. Listing will be provided for all Screened Subjects.

7.2.2. Subject Disposition

The number and relative frequency of subjects of the following will be descriptively summarized using Safety Analysis Set:

- Subjects with ongoing or discontinued WTX-330 treatment
- Subjects who ongoing or discontinued the study
- Reasons for WTX-330 discontinuation
 - Adverse Event
 - Death
 - Physician Decision
 - Pregnancy
 - Progressive Disease
 - Radiographic
 - Clinical
 - Study Terminated by Sponsor
 - Withdrawal of ICF
 - Other
- Reasons for end of study
 - Completed study
 - Withdrawal of Consent by Patient
 - Lost to Follow-Up
 - Death
 - Sponsor Terminated by Sponsor
 - COVID-19 Related
 - Other

Percentages will be calculated with based on the number of subjects in the Safety Analysis Set. Disposition of subjects will be provided in a data listing for the Safety Analysis Set.

7.2.3. Protocol Deviations

Protocol Deviation Management Plan (PDMP) version: 1.0 dated on 23Sep22 defined the study specific procedures and responsibilities for managing Protocol Deviations. The document listed the definition of

QMS Document Name: Statistical Analysis Plan Template(EN)	Page 13 of 41
QMS No (include version ref): STF-015-GL.03	Document date: 14JUL2022
CONFIDENTIAL	

Bioclinica Deviation Description and Deviation Area, as well the Deviation Category (major vs minor). Subject level protocol deviations will be documented in the Clinical Trial Management System (CTMS).

Deviations from the clinical protocol may include, but are not limited to:

- ICF/Subject Information
- Ineligible Subject Enrolled
- IMP Dose Error
- IMP Other Error
- Prohibited Medication
- Procedure/ Test Not Done
- Procedure/ Test Out of Window
- Procedure/ Test Not Performed per Protocol
- Visit Out of Window
- SAE or AESI Reporting Failure
- Other

The number and percentage of subjects with any protocol deviation, major protocol deviation, or minor protocol deviation will be summarized using the Safety Analysis Set separately.

7.3. Demographics and Baseline Disease Characteristics

Demographic and baseline disease characteristics as specified in detail below will be presented descriptively using the Safety Analysis Set.

7.3.1. Demographics and General Baseline Characteristics

The following baseline characteristics will be descriptively (n, mean, Mean, Standard Deviation, Median, Min, Max) summarized using the Safety Analysis Set:

- Age at informed consent (years)
- Weight (kg) at baseline
- Height (cm) at baseline

The number and percentage of subjects under each of the following baseline characteristics will be summarized using the Safety Analysis Set:

- Sex (Female [with childbearing potential, without childbearing potential], Male)
- Age group (<45, 45 through 65, and \geq 65)
- Race (American Indian or Alaska Native, Asian, Black or African American, Native Hawaiian or Other Pacific Islander, White, Other, and Unknown)
- Ethnicity (Hispanic or Latino, Not Hispanic or Latino, and Unknown)
- Eastern Cooperative Oncology Group (ECOG) performance status (0, 1)

7.3.2. Cancer History

The following cancer history characteristics of solid tumor will be summarized descriptively (n, mean, Mean, Standard Deviation, Median, Min, Max) using the Safety Analysis Set:

- Time since date of initial histopathological diagnosis (months) = (date of first dose - date of initial histopathological diagnosis)/30.4375
- Time since date of most recent disease recurrence/progression (months) = (date of first dose - date of most recent disease recurrence/progression)/30.4375

The number and percentage of subjects with the following primary and metastatic cancer history for solid tumor will be summarized using the Safety Analysis Set:

QMS Document Name: Statistical Analysis Plan Template(EN)	Page 14 of 41
QMS No (include version ref): STF-015-GL.03	Document date: 14JUL2022
CONFIDENTIAL	

- Time since date of initial histopathological diagnosis (<12 months, >=12 months - < 24 months, >=24 months - < 36 months, >=36 months)
- Cancer type as recorded in eCRF
- Primary site of solid tumor as recorded in eCRF
- Any pathologic sub-type (Yes, No)
- Stage of solid tumor at initial diagnosis (0, I, II, III, IV)
- Stage of solid tumor at baseline (0, I, II, III, IV)
- Characterization of disease at study entry (locally advanced, metastatic)
- Metastatic site as recorded in eCRF
- Any known genetic mutations (Yes [BRAF, EGFR, HER2, KRAS, KIT, PDGFRA, PIK3CA, NRAS, VHL, Other], No)
- MSI status (Known [MSI-H, MSI-L, MSS dMMR, pMMR] Unknown, Not Applicable)
- TMB Status Known? (No, Not Applicable, Yes [High, Intermediate, Other])
- Tumoral genetic characterization (Yes, No, Not Applicable)

The following cancer history characteristics of lymphoma will be summarized descriptively (n, mean, Mean, Standard Deviation, Median, Min, Max) using the Safety Analysis Set:

- Time since date of diagnosis (months) = (date of first dose - date of initial diagnosis)/30.4375
- Time since date of transformation (months) = (date of first dose - date of transformation)/30.4375

The number and percentage of subjects with the following cancer history for lymphoma will be summarized using the Safety Analysis Set:

- Time since date of diagnosis (<12 months, >=12 months - < 24 months, >=24 months - < 36 months, >=36 months)
- Disease at screening as recorded in eCRF
- Current disease stage (I, IE, II, IIE, II BULKY, III, IV)
- Current Ann Arbor Staging (Stage I, Stage IE, Stage II, Stage IIE, Stage III, Stage IIIE, Stage IIIS, Stage IIIE/S, Stage IV, Not Applicable)
- Bone Marrow Involvement? (Yes, No)

Cancer history characteristics will also be provided in a data listing using the Safety Analysis Set.

7.3.3. Prior Cancer Therapy

Prior cancer therapy information will be summarized using descriptive statistics. Denominators for calculating percentages will be based on the number of subjects in the Safety Analysis Set. Summaries will include the following:

- Any prior anti-cancer therapy
- Type of prior anti-cancer therapy (Surgery, Radiation therapy, Systemic therapy)
- Type of Systemic Therapy (Chemotherapy, Immunotherapy, Hormonal therapy, Targeted therapy, Other)
- Systemic therapy setting (Advance/metastatic, Palliative, Other)
- Best overall response across all prior systemic therapies (CR, PR, SD, PD, NE, NA, Unknown)
- Best overall response from the latest prior systemic therapy (CR, PR, SD, PD, NE, NA, Unknown)
- Reason for stopping treatment in the latest prior systemic therapy (Treatment completed, Progressive disease, Toxicity, Adverse event, Other)
- Number of line of therapies (0, 1, 2, 3, ≥4)

QMS Document Name: Statistical Analysis Plan Template(EN)	Page 15 of 41
QMS No (include version ref): STF-015-GL.03	Document date: 14JUL2022
CONFIDENTIAL	

Time since the last prior systemic therapy started (months, date of first dose – start date of the last prior systemic therapy)/30.4375) will be descriptively (n, mean, Mean, Standard Deviation, Median, Min, Max) summarized using the Safety Analysis Set:

Prior systemic anti-cancer medications will be coded according to the latest version of World Health Organization drug dictionary (WHODRUG Global B3 March 2023) and stored with ATC categories and preferred names (PN). A primary ATC category will be selected before DBL based on considerations such as indication, route of administration, and dosage.

The number and percentage of subjects with medication use coded to each primary ATC level 2 category and preferred name (PN) combination will be summarized descriptively using the Safety Analysis Set. If a subject has received more than 1 drug within an ATC class or PN, the subject will be counted only once for this ATC class or PN.

Prior cancer therapy will be reported in data listings using the Safety Analysis Set.

7.3.4. General Medical History

The medical conditions will be coded according to Medical Dictionary for Regulatory Activities (MedDRA 26.0) according to the Data Management Plan.

The number and percentage of subjects with conditions coded to each primary system organ class (SOCs) and preferred terms (PTs) will be summarized descriptively using the Safety Analysis Set. If a subject has more than 1 medical condition within an SOC or PT, the subject will be counted only once for the respective SOC or PT.

Data listings of all medical history records will be provided using the Safety Analysis Set.

7.4. Prior Non-cancer Therapies & Concomitant Therapies

7.4.1. Prior and Concomitant Medications

Prior and concomitant medications will be coded according to the latest version of World Health Organization drug dictionary (WHODRUG Global B3 March 2023) according to the Data Management Plan and stored with ATC categories and preferred names (PN). A primary ATC category will be selected before DBL based on considerations such as indication, route of administration, and dosage. For classification of prior and concomitant use and the imputation of (partial) missing dates, refer to Subsections 15.5 and 15.6. Prior medication is the medication that stopped before the first dose of WTX-330. Concomitant medication is the medication that are used on/after the first dose of WTX-330.

The number and percentage of subjects with medication use coded to each primary ATC level 2 category and preferred name (PN) combination will be summarized descriptively using the Safety Analysis Set as described. If a subject has received more than 1 drug within an ATC class or PN, the subject will be counted only once for this ATC class or PN. For medications with a common PN but being used in different scenarios with different primary ATC level 2 categories, the PN needs to be summarized under all these ATC level categories.

Prior and concomitant medications information will also be provided in a data listing using the Safety Analysis Set.

7.4.2. Prior and Concurrent Procedures

Prior and concomitant procedure information will also be provided in a data listing using the Safety Analysis Set.

QMS Document Name: Statistical Analysis Plan Template(EN)	Page 16 of 41
QMS No (include version ref): STF-015-GL.03	Document date: 14JUL2022
CONFIDENTIAL	

7.5. Exposure and Compliance

The following exposure and compliance summaries will be derived for each subject for WTX-330:

- Duration of exposure (weeks) is (the date of last administration of WTX-330 – the date of first administration of WTX-330 + 14)/7.
- Total Planned Dose (mg/kg) is calculated by sum of the individual Planned Dose Level being reported in eCRFs.
- Cumulative Dose (mg/kg) is calculated by sum of the individual Total Dose Administered being reported in eCRFs.
- Treatment compliance (%) is 100*(Cumulative Dose/Total Planned Dose) .
- Average Dose Intensity (mg/kg) /cycle) is calculated by Cumulative Dose / number of treatment cycles started (any amount of the study drug was administered)

The duration of exposure (weeks), number of treatment cycle started, and number of study drug infusions, cumulative Dose, Treatment Compliance and Average Dose Intensity will be summarized using descriptive statistics as numerical variables; percent compliance will also be summarized as a categorical variable (<80%, 80-120%, ≥120%); duration of exposure will also be summarized as a categorical variable (<4 weeks, 4 to <12 weeks, ≥12 weeks).

Additionally, the number and percentage of subjects with 0, 1, 2, or ≥3 WTX-330 infusion interruption events and reason for infusion interruption (Infusion Reaction, Adverse Event other than Infusion Reaction, Other) will be summarized; the number and percentage of subjects with WTX-330 dose adjustment (Dose Missed, Dose Reduced, Dose Discontinued, Dose Interrupted) and reason for WTX-330 dose adjustment (Adverse Event, PI/Sponsor Decision, Other) will be summarized.

Exposure, dosage, and compliance data will be presented in a data listing.

8. Efficacy Analyses

8.1. Overview of Planned Efficacy Analyses

All analyses of efficacy outcomes will be primarily based on the Efficacy-Evaluable Set.

Table 1 Overview of Planned Efficacy Analyses

	Data Displays Generated		
	Table	Figure	Listing
Target Lesion Size and Individual Assessment			
Spider (line) plot of percent CFB of sum of target lesion diameters (Solid tumors)		Y	Y
Spider (line) plot of percent CFB of sum of the product of the diameters (Lymphomas)			
Waterfall plot of best percent CFB of sum of target lesion diameters (Solid tumors)		Y	
Waterfall plot of best percent CFB of sum of the product of the diameters (Lymphomas)			
Swimming lane plot of individual time point response assessment and time on treatment		Y	
ORR and iORR			
Number and percentages of subjects in each BOR (iBOR) category	Y		Y
ORR (iORR) and 95% Clopper-Pearson interval			

QMS Document Name: Statistical Analysis Plan Template(EN)	Page 17 of 41
QMS No (include version ref): STF-015-GL.03	Document date: 14JUL2022
CONFIDENTIAL	

		Data Displays Generated		
		Table	Figure	Listing
CBR and iCBR				
CBR (iCBR) at 3, 6, and 9 months		Y		Y
DOR and iDOR				
Number of responders				
Number of events				
Number of censored observations				
Kaplan-Meier estimates of survivor function at landmark time points and associated asymptotic 95% CI	Y			Y
Estimated quartiles of DOR (iDOR) and associated asymptotic 95% CI				
PFS and iPFS				
Number of events				
Number of censored observations				
Kaplan-Meier estimates of survivor function at landmark time points and associated asymptotic 95% CI	Y	Y		Y
Estimated quartiles of PFS (iPFS) and associated asymptotic 95% CI				
OS				
Number of deaths				
Number of censored observations				
Kaplan-Meier estimates of survivor function at landmark time points and associated asymptotic 95% CI	Y	Y		Y
Estimated quartiles of OS and associated asymptotic 95% CI				

8.2. Definitions of Efficacy Outcome Variables

Solid tumors

Assessment of solid tumors will be based on RECIST 1.1 and iRECIST during Screening within 28 days of Cycle 1 Day 1. On-study scans should be performed every 8 weeks (± 7 days) from Cycle 1 Day 1 for the first 6 cycles and every 12 weeks (± 7 days) thereafter. Disease assessments will include radiographic measurements of tumors using computed tomography (CT), magnetic resonance imaging (MRI), or positron emission tomography (PET)/CT. The modality for screening/baseline imaging will be used until progressive disease (PD) per RECIST 1.1 and confirmed progressive disease iRECIST (iCPD) for solid tumor, withdrawal of consent, or initiation of a new anticancer therapy.

Lymphomas

Assessment of lymphomas (NHL) in Dose Expansion Part B will be based on Lugano classification during Screening within 28 days of Cycle 1 Day 1. On-study scans should be performed every 8 weeks (± 7 days) from Cycle 1 Day 1 for the first 6 cycles and every 12 weeks (± 7 days) thereafter. At Screening, lymphoma patients with FDG-avid disease will undergo fluorodeoxyglucose (FDG) PET/CT imaging. All subsequent disease assessments should also be performed with FDG PET/CT, using the Deauville 5-point scale. The avidity of up to six of the largest dominant nodes, nodal masses and/or extranodal lesions, selected to be clearly measurable in two diameters, should be assessed. Nodes should preferably be from disparate regions of the body and should include, where applicable, mediastinal and retroperitoneal areas. Non-nodal lesions include those in solid organs, the GI tract, cutaneous lesions, or those noted on palpation. Non-measured lesions are any disease not selected as dominant or measurable. For patients with non-FDG-avid or variably FDG-avid tumors, a CT scan of the chest/abdomen/pelvis and any additional known sites of disease will be

QMS Document Name: Statistical Analysis Plan Template(EN)	Page 18 of 41
QMS No (include version ref): STF-015-GL.03	Document date: 14JUL2022
CONFIDENTIAL	

performed with IV contrast. The modality for screening/baseline imaging will be used until progressive disease (PD) per Lugano, withdrawal of consent, or initiation of a new anticancer therapy.

8.2.1. Individual Time Point Response

According to RECIST 1.1, the time point response will be evaluated as Complete Response (CR), Partial Response (PR), Stable Disease (SD), Progressive Disease (PD), Not Evaluable (NE). According to iRECIST, the time point response will be evaluated as Immune unconfirmed progressive disease (iUPD), Immune confirmed progressive disease (iCPD), Immune complete response (iCR), Immune partial response (iPR), Immune stable disease (iSD), Not Evaluable (NE). According to Lugano classification, the Lugano (Metabolic/PET-CT Based) time point response will be evaluated as Complete Response (CR), Partial Remission/Response (PR), Stable Disease (SD), and Progressive Disease (PD).

The following RECIST 1.1, iRECIST 1.1, and Lugano time point response(s) will be excluded from derivation of Best Overall Response (BOR), Clinical Benefit Rate (CBR), Duration of Response (DOR), Progression free Survival (PFS), Immuno Best Overall Response (iBOR), Immuno Clinical Benefit Rate (iCBR); Immuno Duration of Response (iDOR), Immuno Progression free Survival (iPFS):

- All RECIST 1.1, iRECIST 1.1 and Lugano time point response(s) after Antineoplastic therapy (including radiotherapy, surgery and medication) will be excluded
- For RECIST 1.1 and Lugano, any time point response(s) after the first PD will be excluded
- For iRECIST, any time point response(s) after the first iCPD will be excluded

8.2.3. Overall Response Rate

Overall response rate (ORR) per RECIST 1.1 and per Lugano is defined as the proportion of subjects achieving CR or PR of BOR.

Immune Overall response rate (iORR) per iRECIST 1.1 is defined as the proportion of subjects achieving iCR or iPR of iBOR.

8.2.4. Clinical Benefit and Clinical Benefit Rate

Clinical benefit for 3, 6, and 9 months based on RECIST 1.1 and Lugano is defined as the subject achieving CR, PR, or SD with duration \geq 3, 6, and 9 months after the date of first dose, respectively. Duration will be calculated as (the date of last CP/PR/SD, whichever occurs late) – date of first WTX-330 dose + 1)/30.4375.

Immuno Clinical benefit for 3, 6, and 9 months based on iRECIST 1.1 is defined as the subject achieving iCR, iPR, or iSD with duration \geq 3, 6, and 9 months, respectively. Duration will be calculated as (the date of last iCP/iPR/iSD – date of first WTX-330 dose + 1)/30.4375.

Clinical Benefit Rate (CBR) or Immuno Clinical Benefit Rate (iCBR) is defined as the proportion of subjects achieving clinical benefit, which will be summarized for 3, 6, and 9 months: CBR3, CBR6, CBR9, iCBR3, iCBR6, and iCBR9.

8.2.5. Duration of Response

Duration of response (DOR), reported the subjects achieving confirmed PR or CR per RECIST 1.1, is calculated from the date of first observation of CR or PR to the date of disease progression using RECIST 1.1 criteria or death, whichever occurs first. The subjects without disease progression or death will be censored on the date of last disease assessment. See below for event/censoring rules.

Situation	Date of Event or Censoring	Event or Censoring
** using the derived dataset as described in section 8.2.1		
Progression after one or none missing assessment	Date of progression	Event
Death after one or none missing assessment	Date of death	Event
No progression (or death)	Date of last assessment	Censored
Progression or death after two or more missing assessment	Date of last assessment prior to missed assessments	Censored

Duration of response (DOR), reported the subjects achieving CR or PR of BOR per Lugano, is calculated from the date of first observation of CR or PR to the date of disease progression using RECIST 1.1 criteria or death, whichever occurs first. The subjects without disease progression or death will be censored on the date of last disease assessment. See above for event/censoring rules.

Immuno Duration of response (iDOR), reported the subjects achieving iCR or iPR per iRECIST, is calculated from the date of first observation of iCR or iPR to the date of first iUPD that is confirmed in subsequent assessments (iCPD), the date of first iUPD that is not followed any of iSD/iPR/iCR in subsequent assessments, or death, whichever occurs first. The subjects without iUPD/death, or with iUPD being annulled by subsequent assessments (iSD, iPR, iCR) will be censored at the date of last assessment.

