8.2.6. Progression-free Survival

Progression-free Survival (PFS) per RECIST 1.1 and Lugano is calculated from the date of first WTX-330 dose to the date of disease progression or death, whichever occurs first. The subjects without disease progression or death will be censored on the date of last disease assessment. See event/censoring rules in section 8.2.5.

Immuno Progression-free Survival (iPFS) per iRECIST, is calculated from the date of first WTX-330 dose to the date of first iUPD that is confirmed in subsequent assessments (iCPD), the date of first iUPD that is

QMS Document Name: Statistical Analysis Plan Template(EN)	Page 20 of 41
QMS No (include version ref): STF-015-GL.03	Document date: 14JUL2022
CONFIDENTIAL	

not followed any of iSD/iPR/iCR in subsequent assessments, or death, whichever occurs first. The subjects without iUPD/death, or with iUPD being annulled by subsequent assessments (iSD, iPR, iCR) will be censored at the date of last assessment.

Alive subjects without postbaseline assessment will be censored at the date of first WTX-330 dose (day 1).

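### SAP 8.2.5 and 8.2.6 do not require an evaluable assessment, so as written a Not Evaluable scan can set the PFS/DOR censor date and escape the missed-assessment rule

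*SAP*

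**What the plan says.** **Censor date.** SAP 8.2.5 states for RECIST 1.1 DOR: "The subjects without disease progression or death will be censored on the date of last disease assessment". SAP 8.2.6 repeats this for PFS and refers back to the 8.2.5 table.

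**Data behind the table.** The table carries the note "using the derived dataset as described in section 8.2.1". Section 8.2.1 defines the RECIST 1.1 categories: "the time point response will be evaluated as Complete Response (CR), Partial Response (PR), Stable Disease (SD), Progressive Disease (PD), Not Evaluable (NE". It also lists NE for iRECIST. The Lugano list there has no NE category.

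**What 8.2.1 removes.** There are three exclusions. The first is any "time point response(s) after Antineoplastic therapy (including radiotherapy, surgery and medication) will be excluded". The second reads "For RECIST 1.1 and Lugano, any time point response(s) after the first PD will be excluded". The third does the same for iRECIST after the first iCPD. None mentions NE.

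**Missed assessments.** A later progression counts under the row "Progression after one or none missing assessment", and death is handled the same way. After two or more missing assessments, the patient is censored at the last assessment before the gap. The word missing is not defined.

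**No post-baseline scan.** SAP 8.2.6 says: "Alive subjects without postbaseline assessment will be censored at the date of first WTX-330 dose (day 1".

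**Elsewhere.** SAP 8.2.4 measures clinical benefit to the last CR, PR or SD. The protocol synopsis (Efficacy Analyses) censors PFS at the last available tumor assessment and is also silent on NE.

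**The concern.** A PFS or DOR time should end where the patient was last known to be free of progression. An overall response of NE does not record that. If an NE visit can be the last assessment, follow-up is credited beyond the last informative scan.

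The rule on two or more missed assessments keeps progression-free time from being credited across long unobserved gaps. If NE visits count as done, a run of them passes through that rule. A later progression or death is then kept as an event at a late date instead of being censored before the gap. The effect is therefore on event status as well as on time.

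The gap also affects reproducibility: because neither term is defined, two programmers could produce different PFS and DOR values from the same SAP. PFS and DOR are listed among the Part 2 secondary endpoints (SAP 1.2), and per-patient values appear in Listing 16.2.6.1.

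**Working it through.** The documents give no median, event count or NE rate for PFS or DOR, so there is no plan figure to reproduce.

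**Inputs**
- Scans every 8 weeks (±7 days) for six 28-day cycles, then every 12 weeks (SAP 8.2). Six cycles are 6 × 28 / 7 = 24 weeks, so scans fall at weeks 8, 16, 24, 36, 48, 60.
- Month = 30.4375 days, both boundary days counted (SAP Appendix 4). Time in months = (7 × week + 1) / 30.4375.
- Up to 20 patients per expansion arm (SAP 3.2). Landmarks at 3, 6, 9, 12 and 15 months (SAP 8.3.5).
- NE rate: not in the documents. Assumed 5% or 10% of scans, with 20% as a stress value.

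**Step 1. Do NE records stay in?** The table uses the 8.2.1 dataset. The three exclusions there concern new therapy, first PD and first iCPD. An NE record before any of these remains.

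**Step 2. Individual records**

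| Record (RECIST 1.1) | As written | NE not counted as an assessment |
|---|---|---|
| SD wk 8, NE wk 16, no more scans, alive | censored wk 16: 113/30.4375 = 3.71 mo | censored wk 8: 57/30.4375 = 1.87 mo |
| SD wk 8, NE wk 16 and 24, PD wk 36 | event wk 36: 253/30.4375 = 8.31 mo | censored wk 8: 1.87 mo |
| SD wk 8, NE wk 16, wk 24 missed, PD wk 36 | event, 8.31 mo (one missing) | censored, 1.87 mo (two missing) |
| Only scan NE at wk 8, alive | censored wk 8: 1.87 mo | Day 1: 1/30.4375 = 0.03 mo |
| SD wk 8, NE wk 16, SD wk 24 | week 24 is the last assessment | same |

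A trailing NE adds 56/30.4375 = 1.84 months in the 8-week phase (42 to 70 days with the visit windows). In the 12-week phase it adds 84/30.4375 = 2.76 months (70 to 98 days).

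**Step 3. Comparison with 8.2.4.** In the first record, clinical benefit lasts to the week 8 SD, 1.87 months, so the patient fails the 3-month criterion. In PFS as written, the same patient is at risk and event-free to 3.71 months, past the 3-month landmark.

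**Step 4. Average size.** Simulation of 100,000 patients per setting, NE at random, exponential progression, mean scan follow-up 30 weeks. Kaplan-Meier estimates, as written vs NE counted as missing:

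| Median PFS | NE rate | Week 16 | Week 26 |
|---|---|---|---|
| 9 wk | 5% | 0.304 vs 0.297 | 0.164 vs 0.159 |
| 9 wk | 10% | 0.319 vs 0.300 | 0.172 vs 0.159 |
| 16 wk | 5% | 0.511 vs 0.505 | 0.362 vs 0.357 |
| 16 wk | 10% | 0.523 vs 0.510 | 0.369 vs 0.356 |

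The differences are 0.6 to 1.9 points at week 16 and 0.5 to 1.3 at week 26. The assumed true values at week 16 are 0.5^(16/9) = 0.292 and 0.5^(16/16) = 0.500, so counting NE as missing lies closer to the truth in all four settings. Between 1.7% and 4.7% of patients change time or status. Per arm that is 20 × 0.017 = 0.34 to 20 × 0.047 = 0.94.

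A second simulation used 800 trials of 20 patients, 5% missed scans, 10% dropout per visit, and true median 2 or 4 months. At 5%, 10% and 20% NE:
- patients changed: 0.4–0.5, 0.8–1.1 and 2.1–2.5 of 20;
- 6-month rate higher as written by about 0.4, 0.7–1.2 and 1.8–3.1 points;
- mean estimated median longer by 0.03–0.09, 0.09–0.13 and 0.23–0.28 months;
- more events as written, for example 16.0 vs 15.6 at 10% NE and median 2 months.

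**The case against.** **The SAP never says that NE counts.** A reader might infer a stated rule; the documents show an omission. Other sections even lean the other way: the confirmation rules in 8.2.2 do not name NE among the interrupting responses, and 8.2.4 ignores NE. This stands as to wording. It does not remove the problem, because 8.2.5 points to a specific dataset and nothing in that dataset's definition drops NE.

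**NE need not mean an unreadable scan.** A reader might infer that an NE visit never carries information. Listing 16.4.6.2 records target, non-target and new-lesion findings separately, so that is not established. An NE followed by an evaluable non-PD scan also does no harm. Both points stand. Still, an overall NE does not document freedom from progression, which is what the censor date should rest on.

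**Day 1 comparison.** A reader might set the NE-only patient against one with no scan, whom 8.2.6 would censor at Day 1. That comparison is not clean. Under SAP section 5, a living patient without progression and without a post-baseline assessment is outside the Efficacy Evaluable Set, and Appendix 6 replaces such a patient in expansion. What remains open is whether an NE-only patient is in that set.

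**Scope.** Lugano PFS and DOR are not reached. For iPFS and iDOR, 8.2.5 and 8.2.6 state no missed-assessment rule, although 8.3.5 lists that censor category for them; only their censor date is at issue here.

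**Size and consequence.** With 20 patients and a rate of 0.3 to 0.5, the binomial standard error is √(0.3 × 0.7/20) = 0.102 to √(0.5 × 0.5/20) = 0.112. A shift of at most 1.9 points is under a fifth of that. Two or more consecutive NE scans before PD occurred in 0.14% to 0.53% of simulated patients, or 0.03 to 0.1 per arm. No efficacy hypothesis test is planned (SAP 2 and 13), the expansion success criterion uses ORR, and the table shells list no PFS or DOR summary table. All of this stands, although SAP 8.1 and 8.3.5 do plan those tables.

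**Conclusion.** The point holds as a defect in the censoring definition for RECIST 1.1 PFS and DOR, and for the censor date of iPFS and iDOR. Followed as written, the SAP lets an NE scan extend follow-up and keeps it out of the missed-assessment count, which is at odds with 8.2.4.

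For an individual patient the change is 8 or 12 weeks for a trailing NE. It is 28 weeks plus a change from censored to event in the rare case of NE at weeks 16 and 24 before PD at week 36. On average it is small: roughly 0.5 to 2 points on PFS rates and about one patient or fewer per arm of 20, at assumed NE rates of 5% to 10% occurring at random. At an assumed 20% it reaches about 3 points. The documents do not support reading this as a material inflation of the trial's efficacy results. It is worth correcting because the correction is nearly free and removes an ambiguity.

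**What to change.** 1. In SAP 8.2.5 and 8.2.6, censor at the last evaluable disease assessment, defined as a time point response other than NE.
2. In the 8.2.5 table, state that an NE time point counts as a missing assessment for RECIST 1.1 PFS and DOR, and censor at the last non-NE assessment before the gap.
3. Extend the Day 1 sentence in 8.2.6 to living patients whose only post-baseline scans are NE, and state in section 5 whether such patients belong in the Efficacy Evaluable Set.
4. Use the last non-NE assessment as the censor date for iPFS and iDOR.

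The cost is a few words, one filter in the time-to-event programs, and slightly shorter reported PFS and DOR. Scan schedules and patient care do not change.
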